9.4. Analysis of safety

Safety analysis will be performed on the ES.

Participants who missed reporting events (solicited/unsolicited AEs or concomitant medications) will be treated as participants without the events (solicited/unsolicited AEs or concomitant medications, respectively).

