9.2. Analysis sets

Table 15 Analysis sets

Analysis set	Description
Screened	All participants who were screened for eligibility.
Enrolled Set	
 All participants who entered the study (who were randomized or received study intervention or underwent a post-screening study procedure). Note: screening failures (who never passed screening even if rescreened) and participants screened but never enrolled into the study (Met eligibility but not needed) are excluded from the Enrolled Set as they did not enter the study.
Exposed Set (ES)	All participants with at least 1 dose of any of the 2 study interventions documented. Analysis per group is based on the administered intervention.
Per Protocol Set (PPS)	
All eligible participants from the ES who meet all the following requirements:
 
 who received the study interventions according to their random assignment and the expected study intervention administration schedule (see Table 3 and Table 4), and without intercurrent conditions* that may interfere with immunogenicity and without prohibited concomitant medication/vaccination. . for anti-poliovirus types 1, 2 and 3 analyses at 1 month post Dose 3 of IPV, participants should have pre- and post-vaccination immunogenicity results for at least 1 antigen and should have complied with interval between IPV Dose 3 and the post IPV Dose 3 blood sample. for anti-RV IgA analyses at 1 month post Dose 2 of Rotarix PCV-free, participants should have pre- and post-vaccination immunogenicity results and should have complied with the interval between Rotarix Dose 2 and the post Rotarix PCV-free Dose 2 blood sample.

* immunosuppressive or immunodeficient conditions identified before Visit 7.

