4.1.2. Reactogenicity

Participants without events (solicited/unsolicited AEs or concomitant medications) reported will be treated as participants without the events (solicited/unsolicited AEs or concomitant medications, respectively).

Refer to Section 6.2.4.2 for the intensity grading of solicited AEs.

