4.5. Safety Analyses

The analyses will be descriptive and conducted on the ES.

The following calculations will be performed for each group:

- The percentage of doses and participants reporting at least 1 AE (solicited or unsolicited) during the 14-day (Day 1 to Day 14) solicited follow-up period will be computed, along with exact 95% CI. The same calculations will be done for AEs (solicited or unsolicited) rated as grade 3 in intensity and for AEs leading to a medically attended visit.
- The percentage of doses over the study and the percentage of participants (by dose and over the study) reporting each individual solicited systemic event will be computed, over the 14-day (Day 1 to Day 14) solicited follow-up period, following study intervention administration, along with exact 95% CI. The same calculations will be done for each individual solicited systemic event rated as grade 3 (grade 3 or grade 4 for fever) in intensity and events leading to a medically attended visit. Temperature above specific thresholds will also be summarized with threshold defined by half degree increment.

Note: Intensity of fever will be assessed by considering the grading scales recommended by the Chinese authorities [NMPA, 2019].

- The verbatim reports of unsolicited AEs will be reviewed by a physician and will be coded according to MedDRA. Every verbatim term will be matched with the appropriate Preferred Term. The percentage of participants with unsolicited AEs occurring within 31-day (Day 1 to Day 31) follow-up period after any dose of *Rotarix* PCV-free with its exact 95% CI will be tabulated by Preferred Term. The same calculations will be done for each AE rated as grade 3 in intensity, for AEs leading to a medically attended visit and for AEs causally related to HRV as per the investigator assessment.
- The percentage of participants reporting the occurrence of SAEs (any, related, fatal, fatal related) from Dose 1 of the study intervention up to study end with its exact 95% CI will be tabulated by study group and by preferred term.
- The percentage of participants reporting the occurrence of SAEs (any, related, fatal, fatal related) within 31-day (Day 1 to Day 31) follow-up period after any dose with its exact 95% CI will be tabulated by study group and by preferred term.
- SAEs and dropouts due to AEs will be described in detail.

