6.2.4.2. Daily recording of solicited AEs

When a specific solicited AE is marked as having not occurred following a specific vaccination (i.e. SDTM CE.CEOCCUR=N for the specified post-vaccination period for the solicited AE in question), all daily measurements will be imputed as Grade 0.

When a specific solicited AE is marked as having occurred following a specific vaccination (i.e. SDTM CE.CEOCCUR=Y for the specified post-vaccination period for the solicited AE in question), any missing daily recordings will be given an imputed value which allows them to contribute to the 'Any' rows but not to specific grade rows of the solicited AE summary tables.

When the occurrence of a specific solicited AE is not present (i.e. SDTM CE.CEOCCUR is neither Y nor N for the specified post-vaccination period for the solicited AE in question) all missing daily recordings will be given an imputed value which allows them to contribute to the 'Any' rows but not to specific grade rows of the solicited AE summary tables.

The following table shows how solicited events are coded for intensity.

Table 6 Intensity scales for solicited AEs – Attribution for codes for Diarrhea, Vomiting and Fever

Event	Infant		
	Intensity grade (Collected or measured)	Intensity grade (code attributed)	Parameter
Loss of appetite	0	0	Appetite as usual
	1	1	Eating less than usual/no effect on normal activity
	2	2	Eating less than usual/interferes with normal activity
	3	3	Not eating at all
Irritability/Fussiness	0	0	Behavior as usual
	1	1	Crying more than usual/no effect on normal activity
	2	2	Crying more than usual/interferes with normal activity
	3	3	Crying that cannot be comforted/prevents normal activity
Cough/runny nose	0	0	Normal
	1	1	Cough/runny nose which is easily tolerated
	2	2	Cough/runny nose which interferes with daily activity
	3	3	Cough/runny nose which prevents daily activity
Diarrhea	looser than normal stools/day	0	Normal (0-2 looser than normal stools/day)
		1	3 looser than normal stools/day
		2	4-5 looser than normal stools/day
		3	≥ 6 looser than normal stools/day
Vomiting	episodes of vomiting/day	0	Normal (no emesis)
		1	1 episode of vomiting/day
		2	2 episodes of vomiting/day
		3	≥3 episodes of vomiting/day
Fever ⁺	Axillary Temperature (°C)	0	Normal (< 37.5°C)
		1	37.5°C – < 38.0°C
		2	38.0°C – < 39.5°C
		3	≥ 39.5°C
		4	≥ 39.5°C, lasts more than 5 consecutive days

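### The plan gives conflicting rules for infants with no solicited data after a dose, so the 'Any' rate is undetermined and graded rates are understated

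*Protocol*

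**What the plan says.** Three provisions bear on an infant with no solicited data after a dose.

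1. **Event-free rule.** Protocol 9.4: "Participants who missed reporting events (solicited/unsolicited AEs or concomitant medications) will be treated as participants without the events". SAP 4.1.2 has nearly the same sentence: "Participants without events (solicited/unsolicited AEs or concomitant medications) reported will be treated as participants without the events". Protocol 9.4 also says "Safety analysis will be performed on the ES", and Protocol 9.2 defines that set as "All participants with at least 1 dose of any of the 2 study interventions documented". SAP 4.5 uses the same set. Neither document defines a denominator restricted to participants or doses with solicited data.

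2. **Imputation rule.** SAP 6.2.4.2 covers the case where "SDTM CE.CEOCCUR is neither Y nor N for the specified post-vaccination period for the solicited AE in question". There, "all missing daily recordings will be given an imputed value which allows them to contribute to the 'Any' rows but not to specific grade rows".

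3. **Numerator table.** The table at the end of SAP 6.2.4.2 admits a participant to 'Any' on the strength of a missing day only if the event is also marked as present. The graded rows need a recorded grade.

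Two further provisions matter. Protocol 10.3.6.1 has sites pursue unreturned cards by telephone or other means. SAP 6.1.6 plans a compliance table, but as worded it counts returned sheets with at least one documented symptom, so it does not clearly show how many diaries came back.

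**The concern.** Solicited events are captured in a paper diary completed by parents. If the diary for a dose yields nothing, whether the infant reacted is unknown. Provision 1 turns that unknown into a favourable result. Provision 2 turns it into an event in the 'Any' row only. Provision 3 agrees with provision 1 and contradicts provision 2, although it sits in the same SAP section as provision 2.

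Reactogenicity is a stated secondary objective, and the percentages are reported by group with exact 95% intervals. Two programmers following the SAP in good faith could produce different headline rates from the same data. A reader of the report could not tell which rule was used, nor how much data was missing.

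**Working it through.** **Inputs.** Planned group size is 200 (Protocol 4.1, Table 6), all assumed vaccinated. The documents state neither a solicited-event rate nor a diary-return rate, so there is no plan figure on this point to reproduce. The plan's only power figure, 90.4% overall, concerns seroconversion. It equals one minus the sum of the stated type II errors (1 - 0.018 - 0.075 - 0.003 = 0.904), and nothing here depends on it.

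**Assumptions.** Let p be the true proportion with a given solicited event after one dose, taken as 10% to 40%. Let m be the share with no solicited data after that dose, taken as 2% to 20%. Missingness is taken as unrelated to events.

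**Formulas for one dose.**
- Event-free rule: reported 'Any' = p(1-m), a shift of -pm.
- Imputation rule: reported 'Any' = p(1-m) + m, a shift of +m(1-p).
- With-data denominator: reported 'Any' = p.
- A graded row with true rate g: g(1-m) under either stated rule, because infants without data stay in the denominator and never enter a graded numerator.

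**Results with 200 infants.**

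| p | m | No data | Events among those with data | Event-free rule | Imputation rule | With-data denominator |
|---|---|---|---|---|---|---|
| 10% | 10% | 20 | 18 | 18/200 = 9.0% | 38/200 = 19.0% | 18/180 = 10.0% |
| 20% | 5% | 10 | 38 | 38/200 = 19.0% | 48/200 = 24.0% | 38/190 = 20.0% |
| 20% | 20% | 40 | 32 | 32/200 = 16.0% | 72/200 = 36.0% | 32/160 = 20.0% |
| 40% | 20% | 40 | 64 | 64/200 = 32.0% | 104/200 = 52.0% | 64/160 = 40.0% |

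In the first row the exact 95% interval is 5.4% to 13.9% under the event-free rule and 6.0% to 15.3% with the with-data denominator.

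**Range over the assumed grid.** The downward shift runs from 0.10 × 0.02 = 0.2 points to 0.40 × 0.20 = 8 points. The upward shift runs from 0.02 × 0.60 = 1.2 points to 0.20 × 0.90 = 18 points. A Grade 3 rate falls by the relative amount m under both stated rules. At m = 10%, it is reported at 0.9 of its true value.

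**Limit of the formula.** It applies dose by dose. In an over-study row, an infant who loses one card may still be counted from another. For example, suppose 30% of infants react after both of two doses and each card is lost independently with probability 20%. The event-free rule then reports 0.30 × (1 - 0.20 × 0.20) = 28.8%, not 0.30 × 0.80 = 24.0%.

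**The case against.** The strongest reply is that the SAP has a specific rule for unknown occurrence, and that a specific derivation rule should override a general sentence. If so, missing diaries raise the 'Any' rate, and a charge of favourable scoring fails for that row. This stands as far as it goes: a reader might infer from Protocol 9.4 alone that every solicited percentage is understated, and the documents do not support that. But the reply does not settle which rule applies, because the numerator table in the same section contradicts the imputation rule. Nor does it help the graded rows.

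It is also fair to say that neither general sentence mentions unreturned cards. Their inclusion is inferred from the wording together with an Exposed Set that has no diary requirement.

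Two stronger readings should be resisted:
- A reader might cite Amendment 1 as evidence that cards will be lost. The risk it describes belongs to the superseded arrangement of handing out the diary at the first visit and collecting it at the last. The amendment was made to remedy that, and Protocol 10.3.6.1 adds active retrieval. Retrieval reduces loss, but it does not say how any remaining loss is analysed.
- A reader might infer bias between arms because Staggered infants have four cards (Visits 1 to 4) and Co-administration infants two (Visits 2 and 4). Nothing in the documents shows that loss per card differs, and the planned safety calculations are within group and descriptive.

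**Conclusion.** The concern holds as a conflict between rules. Protocol 9.4, SAP 4.1.2 and the numerator table point one way, and the imputation text in SAP 6.2.4.2 points the other. For the 'Any' row, even the direction of the error depends on which is programmed: 0.2 to 8 points down, or 1.2 to 18 points up, over the assumed range. Grade 3 rows are lowered under either rule, by the relative amount m.

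These sizes rest on assumed p and m and on missingness unrelated to events. If no infant without data had an event, the event-free rule would do no harm. If return is near complete, all three approaches agree closely. The effect is confined to descriptive secondary safety estimates. The point is worth correcting because the remedy is simple and the present text leaves the headline rate undefined.

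**What to change.** 1. For solicited events, use as denominator the Exposed Set participants (or doses) with at least one documented diary day, or a yes/no occurrence answer, after that dose.
2. Align Protocol 9.4, SAP 4.1.2, SAP 4.5, the imputation text in SAP 6.2.4.2 and its numerator table to this one rule. Changing 4.1.2 and 4.5 alone is not enough: an infant with one documented day and no yes/no answer would enter the new denominator and could still be imputed into 'Any'.
3. Keep the no-report-means-no-event rule only for unsolicited adverse events and concomitant medications.
4. In SAP 6.1.6, tabulate plain diary return by group and dose, whether or not a symptom was recorded.
5. Show results with missing as no event and missing as event as bounds.
6. Unless Protocol 9.4 is amended, declare the departure in SAP 4.8, which now states that there are no changes.

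**Cost.** Text changes in the SAP, a protocol change or declared departure, a denominator flag and a few extra table rows. No new data are needed. Denominators become slightly smaller, and the main estimate assumes that missing diaries are unrelated to events. The bounds in item 5 show how far that assumption matters.

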9.4.1. Within groups assessment

The following calculations will be performed for each group:

- The percentage of doses and participants reporting at least 1 AE (solicited or unsolicited) during the 14-day (Day 1 to Day 14) solicited follow-up period will be computed, along with exact 95% CI. The same calculations will be done for AEs (solicited or unsolicited) rated as Grade 3 in intensity and for AEs leading to a medically attended visit.
- The percentage of doses and participants reporting each individual solicited systemic event will be computed, over the 14-day (Day 1 to Day 14) solicited follow-up period, following study intervention administration, along with exact 95% CI. The same calculations will be done for each individual solicited systemic event rated as Grade 3 in intensity and events leading to a medically attended visit. Temperature above specific thresholds will also be summarized with threshold defined by half degree increment.

Note: Intensity of fever will be assessed by considering the grading scales recommended by the Chinese authorities [[NMPA, 2019b](#)].

- The verbatim reports of unsolicited AEs will be reviewed by a physician and will be coded according to MedDRA. Every verbatim term will be matched with the appropriate preferred term. The percentage of participants with unsolicited AEs occurring within 31-day (Day 1 to Day 31) follow-up period after any dose with its exact 95% CI will be tabulated by preferred term. The same calculations will be done for each AE rated as Grade 3 in intensity, for AEs leading to a medically attended visit and for AEs causally related to HRV as per the investigator assessment.
- The percentages of participants who started taking at least 1 concomitant medication, by type (any, antipyretic), from Day 1 to Day 14 after study intervention administrations will be tabulated with exact 95% CI. The percentages of participants who started taking at least 1 concomitant medication, by type (any, antipyretic), within 1 month after each dose will also be tabulated with exact 95% CI.
- SAEs and dropouts due to AEs will be described in detail.

9.5. Other analyses

9.5.1. Demographic and baseline characteristics analyses

The median, mean, range and standard deviation of age (in weeks) for each dose of study intervention and for gestational age (in weeks) will be computed by group. Median, mean and standard deviation of height in centimeter and weight in kg at Visit 1 will be computed by group. The geographical ancestry and sex composition will be presented.

9.6. Interim analyses

All analyses will be conducted on final data and therefore no statistical adjustment for interim analyses is required.

9.7. Sample size determination

A maximum of 400 participants (200 in the Co-administration group and 200 in the Staggered group) will be randomized such that approximately 160 evaluable participants complete the study, in each group for the evaluation of the primary objective assuming that approximately 20% of the enrolled participants will not be evaluable.

Participants who withdraw from the study will not be replaced.

The power calculation is based on the positive conversion rates of the Beijing Biological Products Institute Co.,Ltd. IPV, as mentioned in the package insert [[Inactivated Poliomyelitis Vaccine Made From Sabin Strains \(Vero Cells\)](#) package insert, 2019].

The positive conversion rate is defined as the percentage of participants at 1 month post Dose 3 of immunization with:

- Neutralizing antibody titer $\geq 1:8$ for participants with titer $< 1:8$ pre-immunization or
- At least 4 times increase in neutralizing antibody titer for participants with titer $\geq 1:8$ pre-immunization.

The definition of seroconversion used in this protocol differs slightly from the above definition of positive conversion by taking into account the expected decline in maternal antibodies between the pre-vaccination blood sample and the post IPV Dose 3 blood sample. By definition, the seroconversion rate will be at least equal to the positive conversion rate. Therefore, as a worst-case scenario, the observed positive conversion rates are used in the following sample size computations.

The power presented in [Table 16](#) is based on PASS 2019 (one-sided Non-Inferiority Tests for the Difference Between Two Proportions), under the alternative hypothesis of a 96.23% (Polio 1), 93.83% (Polio 2), and 97.60% (Polio 3) seroconversion rate for the Staggered group and a true difference of 0% between the Co-administration group and Staggered group, using Miettinen and Nurminen's Likelihood Score Test of the Difference. Under these conservative assumptions the overall power is above 90.4% (i.e., global type II error is conservatively computed as the sum of nominal type II errors).

Table 16 Probability that the lower limit of the 95% CI around group difference in the percentage of participants with anti-poliovirus types 1, 2 and 3 antibody seroconversion 1 month post Dose 3 of IPV (Co-administration group minus Staggered group) is greater than or equal to -10%

Ag	True seroconversion rate (Co-administration group) *	True seroconversion rate (Staggered group) *	N evaluable (each group)	Power	Alpha
Polio 1	96.23%	96.23%	160	98.2%	0.025
Polio 2	93.83%	93.83%	160	92.5%	0.025
Polio 3	97.60%	97.60%	160	99.7%	0.025
Overall				90.4%	

Ag: Antigen; N: number of participants

* Observed positive conversion rate from the Beijing Biological Products Institute Co.,Ltd. IPV package insert [[Inactivated Poliomyelitis Vaccine Made From Sabin Strains \(Vero Cells\)](#) package insert, 2019].

10. SUPPORTING DOCUMENTATION AND OPERATIONAL CONSIDERATIONS

10.1. Appendix 1: Regulatory, Ethical, and Study Oversight Considerations

10.1.1. Regulatory and ethical considerations

- This study will be conducted in accordance with the protocol and with:
 - Consensus ethical principles derived from international guidelines including the Declaration of Helsinki and Council for International Organizations of Medical Sciences (CIOMS) International Ethical Guidelines
 - Applicable ICH GCP Guidelines
 - Applicable laws and regulations
- The protocol, protocol amendments, ICF, IB, and other relevant documents (e.g., advertisements) must be submitted to an IRB/IEC by the investigator for review and approval. These documents will be signed and dated by the investigator before the study is initiated.
- Any protocol amendments will require IEC/IRB approval before implementation of changes made to the study design, except for changes necessary to eliminate an immediate hazard to study participants.
- GSK will provide full details of the above procedures to the investigator, either verbally, in writing, or both.

- The investigator will be responsible for the following:
 - Providing written summaries of the status of the study to the IRB/IEC annually or more frequently in accordance with the requirements, policies, and procedures established by the IRB/IEC.
 - Notifying the IRB/IEC of SAE(s) or other significant safety findings as required by IRB/IEC procedures.
 - Providing oversight of the conduct of the study at the site and adherence to requirements of 21 CFR, ICH guidelines, the IRB/IEC, European regulation 536/2014 for clinical studies (if applicable), and all other applicable local regulations.

10.1.2. Financial disclosure

Investigators and sub-investigators will provide the sponsor with sufficient, accurate financial information as requested to allow the sponsor to submit complete and accurate financial certification or disclosure statements to the appropriate regulatory authorities. Investigators are responsible for providing information on financial interests during the study and for 1 year after completion of the study.

10.1.3. Informed consent process

The investigator(s) or their representative(s) must fully explain the nature of the study to the participant's parent(s) or participant's LAR(s) and answer all questions regarding the study.

Participants' parent(s)/LAR(s) must be informed that their participation is voluntary.

Freely given and written/witnessed/thumb printed informed consent must be obtained from each participant's parent(s)/LAR(s)/witness as appropriate, prior to participation in the study.

The content of the ICF must meet the requirements of 21 CFR 50, local regulations, ICH guidelines, Health Insurance Portability and Accountability Act (HIPAA) requirements, where applicable, and the IRB/IEC or study center.

The medical record must include a statement that written or witnessed/thumb printed informed consent was obtained before the participant was enrolled in the study and the date the consent was obtained. The authorized person obtaining the informed consent must also sign the ICF.

Participants must be re-consented if a new version of the ICF(s) or an ICF addendum is released during their participation in the study.

A copy of the ICF(s) must be provided to the participants' parent(s)/LAR(s).

If follow-up information from a treating physician or other licensed medical practitioner is required for a medical device incident with an AE/SAE involving an associated person(s), the Associated Person Safety Reporting Information and Authorization Letter must be signed by the associated person to obtain consent.

